2.1.3.2.5 Complications

All complications are recorded as adverse events. Derivation of adverse events and analyses is discussed under safety endpoints and analysis.

This endpoint is at the patient level.

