Rev. 03
Page: 3/4

	
Immediate and postoperative complications including arterial insufficiency, venous congestion, thrombosis, need for surgical re-exploration of anastomosis, partial flap necrosis or flap loss will be recorded. In the case of lymphatic surgery, the Surgeon will use volumetric measurement to assess the procedure impact on lymphedema.
 
All adverse events will be collected from the procedure date to the study exit of each subject enrolled.

Analysis	
The full analysis set (FAS) is defined as all patients enrolled onto the registry who underwent surgery with Symani. The FAS will be sub-divided into three distinct cohorts, depending on the surgery performed (replantation, free flaps, lymphatic surgery).

Follow-Up Schedule	
Assessments will be made intraoperatively and at regular intervals during hospitalization.
 
The study will be considered complete after all patients have completed their follow-up visits as described in the study protocol.

Inclusion and Exclusion Criteria	
Inclusion criteria
 
1) Male and female patients aged >182) Patients who need a reconstructive procedure and a microsurgical reconstruction is deemed the best option by the plastic, orthopedic or other surgeon in response to a post-oncological, post-traumatic or congenital tissue defect or to treat lymphedema.3) Patients who have been selected by the PI at the Clinical Center as appropriate candidates for treatment with Symani System in accordance with the IFU.4) Subjects who fit the criteria to perform surgery requiring reconstructions using free flaps, replantation, lymphatic reconstructions.5) Subjects who agree to have the surgery and the anaesthesia.6) Subjects who voluntarily decide to participate in this study with the surgery performed with the aid of the Symani System and sign the Informed Consent Form. 
Exclusion criteria
 
1) Subjects who have bleeding or coagulation disorders in the past or present.2) Any criteria that preclude prolonged anesthesia.3) History of anaphylaxis or severe complicated allergy symptoms.

**RASM
POST MARKET CLINICAL FOLLOW-UP
STUDY
Synopsis**

CDC-00031
Rev. 03
Page: 4/4

- 4) Clinically significant cardiovascular, digestive, respiratory, endocrine, or central nervous system disorders or previous mental disorders that may significantly affect the data collection or the ability to comply with the protocol.

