2.1.5 Safety endpoints

All adverse events (AE, SAE/ADE/SADE/ADE/DD) reported by patients or evaluated by the Surgeon from day 0 to either 30 days after surgery for free flaps, replantation and other procedures, or 24 weeks after surgery for the LVA procedures will be recorded.

All adverse events will be recorded on an adverse event form in the CRF (form U2 in Dendrite or Repeating Data: Adverse Events in Castor). Adverse events will be coded using MedDRA to obtain system organ class (SOC) and preferred term (PT).

All events are assessed by the surgeon for severity (mild/moderate/severe) and seriousness (serious/not serious). In addition, for each event, the surgeon will answer three questions regarding relationship to the device:

- Related to the device
- Related to device malfunction
- Related to device misuse

For each of these assessments, the response is on a 5 point 'scale', namely:

- Not related
- Unlikely
- Possible
- Probable

Sponsor: MMI Product: Symani system for microsurgical anastomosis Study: PRIMO	
Statistical Analysis Plan Final 22 November 2024	

- Definite OR
- Unassessable

They are also asked to note whether there was a different (not device related) cause.

Treatment initiated (if any) and outcome (resolved, resolved with sequelae, ongoing or death) are also recorded.

Event details are recorded as verbatim text.

A separate form will be completed for each event.

Adverse events of special interest, namely, the AEs cited in the literature (e.g., arterial insufficiency, venous congestion) will be flagged based on MedDRA coding.

No further derivations of adverse events data will be undertaken.

2.1.5.1 Additional safety endpoints not defined in the protocol.

2.1.5.1.1 Freedom from device related serious adverse events prior to discharge.

Dendrite's Form U2, and Castor's Repeating Data Form: Adverse Events, is used to collect adverse event data. If there are any adverse events marked as serious where ANY device related question (see note below) is 'possible', 'probable' or 'definite' the event will be classified as a device related SAE = yes.

If ALL AE forms have full responses to the required questions and the AE is not classified as 'device related SAE'=yes then the patient will be classified as device related SAE=No.

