2.4.6 Analyses of safety data

2.4.6.1 General analyses of adverse events

Summary tables displaying both incidence and number of adverse events (AE) overall, by severity, by relationship to study device, by relationship to study procedures, and by seriousness will be produced. The incidence of AE which are device deficiencies will also be shown. Subset incidence tables will be produced for anticipated AE, and for unanticipated AE.

The overall incidence of any adverse event will be presented with exact 95% confidence limits. The result will be compared descriptively with the 30 day complication rate of 31.6% (95% confidence limits 27.5, 36.0%) reported by Veith et al [2]. The paper by Veith et al has been selected as the literature value for descriptive comparison as it describes complication rate in the 30 day post-operative period; which is the period of observation in the current study. Other than this paper there is limited published information on 30 day complication rates.

For serious AE, frequency tabulations of the reasons for the event being an SAE will be produced. A subset incidence table will be produced for anticipated SAE, and a second subset table for unanticipated SAE.

Tables will be produced for the SAS and by subpopulation (prospective/retrospective).

Sponsor: MMI Product: Symani system for microsurgical anastomosis Study: PRIMO	
Statistical Analysis Plan Final 22 November 2024	

All adverse event data will be shown in patient data listings.

Sponsor: MMI Product: Symani system for microsurgical anastomosis Study: PRIMO	
Statistical Analysis Plan Final 22 November 2024	

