Appendix 1. Summary of endpoints, unit of analysis and analysis method

Endpoint	Level	analysis
Robotic success	Anastomosis	GLMM. Bernoulli form by stype Fixed: recipient site/location, subpop For replantations also include procedure type (free or nerve) Random surgeon, procedure number anastomosis number, subject=patient. Model 1/1a.
Robotic usability	Patient	GLMM Binomial form as nsuccess/npats by stype Fixed: recipient site/location. For replantations also include procedure type (free or nerve) Random surgeon. Model 2./2a
Anastomosis time	Anastomosis	GLMM normal by stype Fixed: recipient site/location, subpop For replantations also include procedure type (free or nerve) Random surgeon, procedure number anastomosis number, subject=patient. Model 3/3a
Intra-operative redo	Anastomosis	Model 1/1a
Post-op redo	Procedure	GLMM Bernoulli form by stype Fixed: recipient site/location, subpop For replantations also include procedure type (free or nerve),

Sponsor: MMI Product: Symani system for microsurgical anastomosis Study: PRIMO	
Statistical Analysis Plan Final 22 November 2024	

		Random surgeon, procedure number subject=patient. Model 4/4a
Complications	Patient	Safety endpoint. Summaries of AEs
Warm ischemia time		
Flap loss/failure	Procedure	Model 4/4a
Limb volume reduction	Procedure	GLMM normal Fixed timepoint. Cov baseline vol. Random surgeon, procedure number subject=patient. Model 5.
Free flap viability at 30 days	Procedure	Model 4/4a
Intra-operative anastomosis patency	Anastomosis	Model 1/1a
Rate of intra-operative approach change	Anastomosis	Model 1/1a
Freedom from device related SAE at discharge	Patient	Simple frequency and exact CL
Freedom from device related AE at discharge	Patient	Simple frequency and exact CL
All cause re-admission rate	Patient	KM. Use PL to get rate within 30 days
All cause re-op rate	Patient	KM. Use PL to get rate within 30 days
All cause mortality rate	Patient	KM. Use PL to get rate within 30 days
Length of hospital stay	Patient	Descriptive stats

PRIMO Statistical Analysis Plan

Final Audit Report

2024-12-13

Created:	2024-12-11
By:	[name] ([contact])
Status:	Signed
Transaction ID:	CBJCHBCAABAAHjF3YtYJkG7xb1_tZngZ89-skKZM8HiF

"PRIMO Statistical Analysis Plan" History

-  Document created by [name] ([contact])
2024-12-11 - 4:57:01 PM GMT
-  Document emailed to [name] ([contact]) for signature
2024-12-11 - 4:57:09 PM GMT
-  Document emailed to [name] ([contact]) for signature

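### The secondary endpoint Complications has no event definition or table of its own in the SAP, and any-adverse-event incidence is what gets compared with a literature complication rate

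*SAP*

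**What the plan says.** The Protocol Synopsis (Secondary Endpoints) lists complications under replantation, free flap and lymphatic surgery, and SAP 1.3.1 repeats this. The synopsis then asks for recording of "Immediate and postoperative complications including arterial insufficiency, venous congestion, thrombosis, need for surgical re-exploration of anastomosis, partial flap necrosis or flap loss". A separate sentence covers adverse events in general: "All adverse events will be collected from the procedure date to the study exit of each subject enrolled".

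SAP 2.1.3.2.5 gives the endpoint at patient level in two statements: "All complications are recorded as adverse events" and "Derivation of adverse events and analyses is discussed under safety endpoints and analysis". The Appendix 1 entry is "Safety endpoint. Summaries of AEs".

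SAP 2.1.5 says that AEs of special interest, described as those cited in the literature, with arterial insufficiency and venous congestion as examples, "will be flagged based on MedDRA coding". It rules out any further derivation from the AE data.

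SAP 2.4.6.1 states: "The overall incidence of any adverse event will be presented with exact 95% confidence limits". That figure is compared descriptively with a 30-day complication rate of 31.6% (27.5% to 36.0%) from a cited study. The AE tables it plans are overall, by severity, by seriousness, by relationship to device and to procedure, for device deficiencies, and for anticipated and unanticipated events.

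**The concern.** That every complication is an AE does not make every AE a complication. The SAP uses the first statement to settle the endpoint and never says which AEs are complications. Two things follow.

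- The protocol asks for complications by surgery type, and the SAP names no analysis that yields a complication rate. The one device that could isolate such events, the special-interest flag, is created and then left unused.
- The figure set against a literature complication rate counts patients with any AE of any cause, so the two sides of the comparison may not measure the same thing. Unrelated minor events can raise the trial's figure, and an excess of thrombosis or venous congestion would be hard to see in an any-AE total.

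The study's stated objective includes monitoring safety, so this is an endpoint that readers will look for.

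**Working it through.** **The plan's own figure.** The count and denominator behind 31.6% are not in the documents, so it cannot be reproduced. It is internally consistent. Exact (Clopper-Pearson) limits round to 27.5% and 36.0% for counts from 149/471 to 155/490, and Wilson limits do so from 143/453 to 146/462. The interval therefore looks like that of a simple proportion. Nothing shows which events it counts.

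**Where each event named in the protocol is analysed.**

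| Event | Planned analysis of its own |
|---|---|
| Arterial insufficiency | None; an example for the flag in 2.1.5 |
| Venous congestion | None; an example for the flag in 2.1.5 |
| Thrombosis | None |
| Re-exploration of anastomosis | 7-day redo (2.4.4.2.4) and 30-day re-operation (2.4.6.2.4) |
| Partial flap necrosis | None; 2.1.3.3.2 scores partial survival as no loss |
| Flap loss | 2.4.4.2.6 and 2.4.4.3.1 |

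Four of the six have no stated patient-level rate. AEs are coded to system organ class and preferred term, but 2.4.6.1 does not list a table by preferred term.

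**Size of the definitional effect.** Let c be the share of patients with a complication, and u the share of complication-free patients who have some other AE. Then

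any-AE incidence = c + (1 − c)u = 1 − (1 − c)(1 − u).

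This is never below c, and it exceeds c whenever u > 0 and c < 1. With u defined in this way no independence assumption is needed. The documents give neither c nor u, so both are assumed. With c = 31.6% and, for illustration, the planned minimum of 402 patients for exact limits:

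| u | Any-AE incidence | Excess over c | Exact 95% limits, n = 402 |
|---|---|---|---|
| 0% | 31.6% | 0 | 27.1% to 36.4% |
| 5% | 1 − 0.684 × 0.95 = 35.0% | 3.4 points | 30.4% to 40.0% |
| 10% | 1 − 0.684 × 0.90 = 38.4% | 6.8 points | 33.8% to 43.5% |
| 20% | 1 − 0.684 × 0.80 = 45.3% | 13.7 points | 40.3% to 50.3% |
| 30% | 1 − 0.684 × 0.70 = 52.1% | 20.5 points | 47.2% to 57.2% |

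The any-AE figure reaches the benchmark's upper limit of 36.0% at u = 1 − 0.640/0.684 = 6.4%.

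**Direction against 31.6%.** Other assumptions give a different picture:

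- c = 20%: any-AE incidence is 1 − 0.80 × 0.90 = 28.0% at u = 10%, and 1 − 0.80 × 0.80 = 36.0% at u = 20%.
- Half the patients lymphatic with a 5% complication rate, the rest at 31.6%: c = 0.5 × 0.316 + 0.5 × 0.05 = 18.3%. At u = 10%, any-AE incidence is 1 − 0.817 × 0.90 = 26.5%.
- Half the patients retrospective with half of affected patients captured, c = 31.6%, u = 10%: 0.5 × 38.4% + 0.5 × 0.5 × 38.4% = 28.8%.

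The AE window of 24 weeks for lymphatic surgery (2.1.5) pushes the other way. It also does not fit the statement in 2.4.6.1 that 30 days is this study's observation period.

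**The case against.** The strongest reply is that the benchmark's definition is unseen. If the cited study counts a broad set of postoperative events, any-AE incidence may be the closer match, and a narrow flagged-event rate could make the device look safer than the literature. This stands, and it rules out simply swapping one numerator for the other.

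The protocol's list is also open: its wording marks the named events as examples. They are mainly flap and vessel events and may be too narrow for lymphatic surgery. The flag in 2.1.5 is tied to the literature, and only two of its terms are shown to overlap with the protocol's. Both points stand and shape the fix.

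Next, the SAP derives no yes/no complication variable, so it does not literally label every AE a complication. That is fair. The defect is a missing rule, together with an any-AE figure used where a complication rate is expected.

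Finally, other analyses help. Re-exploration and flap loss are largely covered, AEs are split by severity, seriousness, relatedness and anticipated status, all AEs are listed, and 2.4.1 identifies surgery-type cohorts. The help is partial. None of these is a patient-level complications table, and none is the figure compared with 31.6%. The AE assessment in 2.1.5 asks about relationship to the device and about another cause, but lists no procedure-relationship question, so the source of that table is unclear. The comparison is descriptive and no decision rule depends on it, which limits the consequence.

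**Conclusion.** The point holds as a gap in definition and tabulation. Followed as written, the SAP yields no complication rate for the secondary endpoint. It states no patient-level rate for arterial insufficiency, venous congestion, thrombosis or partial flap necrosis, and it leaves the special-interest flag unused. Its any-AE figure is at least as high as the trial's own complication rate; the excess is (1 − c)u, or 3.4 to 20.5 points for c = 31.6% and u from 5% to 30%. Those inputs are assumptions, not figures from the documents.

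A reader might infer that the trial's result will be overstated against 31.6%. The documents do not support that. They do not say which events the 31.6% counts. The cited study's title limits it to lower-extremity free flaps, whereas the overall AE figure pools flaps, replantations and lymphatic surgery. SAP 2.5.6 also expects missing data in the retrospective collection, which could lower the observed rate. The supportable conclusion is that the comparison cannot be interpreted as planned. It should be corrected before analysis, but it does not affect the primary endpoint.

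**What to change.** - **2.1.3.2.5:** define a patient as having a complication if at least one AE falls on a prespecified MedDRA term list. Include the protocol's named events and extend the list as needed for replantation and lymphatic surgery. Align the flag in 2.1.5 with this list.
- **2.4.6.1 and Appendix 1:** add a patient-level table of complications by surgery type and subpopulation, with exact 95% limits. Keep the any-AE table.
- **Comparison with 31.6%:** state which events the cited rate counts, match the numerator to those events, ideally in lower-limb free flaps, and show the complication rate and any-AE incidence side by side.

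The cost is SAP wording, a term list to be fixed before analysis, and one or two extra tables from AE data already due to be coded. No new data collection is needed.

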2.1.3.3 Secondary Effectiveness Endpoints - Free Flap and Replantation

2.1.3.3.1 Ischemia time

Warm ischemia time is captured directly on the operation CRF (for free flaps and replantations).

2.1.3.3.2 Free flap failure or loss at discharge/replantation failure or loss (subsequent amputation).

This endpoint only refers to flap procedures or replantations.

The unit of analysis is the flap/replantation, i.e. at the procedure level.

Separate variables will be derived for flaps and replantations.

For each flap, Dendrite’s form H and Castor’s Free Flap Operation Visit operation visit: Operation Data Forms record the answer to the question ‘Flap survival at recipient site at discharge’, with options ‘100% - complete survival’, ‘partial survival’, ‘zero survival’, ‘buried flap’ or ‘unknown’. In Dendrite, the same form is used for replantations, so if the procedure is replantation, then the question will be interpreted as ‘Replantation survival at discharge’.

Each flap will be classified as ‘loss/failure’ = yes if the response to the question is ‘zero survival’ and loss/failure = ‘no’ if the response is ‘100% complete survival’ or ‘Partial survival’. If the response is ‘buried flap’ or ‘unknown’ the response will be missing.

For replantations the options are:

Yes, No, partial failure, not applicable

Sponsor: MMI Product: Symani system for microsurgical anastomosis Study: PRIMO	
Statistical Analysis Plan Final 22 November 2024	

Each replantation will be classified as ‘loss/failure’ = yes if the response to the question is ‘yes’ and loss/failure = ‘no’ if the response is No or ‘Partial failure’. If the response is not applicable the response will be missing.

For both variables, if the question is not answered the variable will be missing.

2.1.3.4 Secondary Effectiveness Endpoints - Lymphatic surgery – limb volume reduction

Limb volume is recorded on the pre-operative limb assessment form and at each follow-up visit.

The change in limb volume will be calculated as:

limb volume at visit_x – limb volume pre-op.

Where x is visit 1 (24 hours post-op), visit 2 (4 days post-op), visit 3 (14 days post-op) or visit 4 (24 weeks post-op). This represents limb volume reduction.

This endpoint is at the procedure level.

2.1.3.5 Additional Effectiveness Endpoint (not defined in protocol)

2.1.3.5.1 Free flap viability at 30 days

For Castor, separate forms are used for free flaps and for replantations. At all follow-up forms for flaps, there is a question ‘flap loss/failure’, with the options Yes or No. For replantations the question relates to replantation failure with the options ‘Yes’, ‘no’, ‘N/A’ or ‘Other’.

To derive the endpoint

For all follow-up forms, the date of follow-up and the date of surgery will be used to determine the time post-surgery. I.e.

follow-up time = date of follow-up visit – date of operation +1 days.

All forms will be considered.

If there is a form where the visit is at least 23 days post index operation, this will be used as the 30 day follow up form.

The following hierarchy will be used to derive the endpoint:

If there is a 30-day follow-up form with a non-missing answer to the question, this response will be used.

Otherwise, if the study termination form (form z in dendrite, termination visit: termination form in castor) indicates the patient did not complete the study and the reason for study exit was patient death, the last recorded flap survival status will be used, regardless of when this was recorded. Note, the reason for withdrawal on form z or termination visit: termination form is free text. However, form u1 or all visit forms record the patient status at

Sponsor: MMI Product: Symani system for microsurgical anastomosis Study: PRIMO	
Statistical Analysis Plan Final 22 November 2024	

discharge (alive/dead) and date of discharge/death. If there is a form u1 or any visit forms (1-4) where status at discharge is dead, the patient will be regarded as died during the study.

Otherwise, if the study termination form notes the patient did not complete the study and the reason for study exit was anything other than death, the last recorded flap survival status will be used, provided the status was recorded ≥ 20 days since the index procedure.

Otherwise, in all other circumstances the endpoint will be set to missing.

For replantations the same approach will be used, however if the response to the question is 'N/a' or 'Other' then failure/loss will be missing.

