2.2.2 Effectiveness populations

2.2.2.1 Full Analysis Set (FAS)

The FAS will comprise patients in the All Enrolled Set for whom a robotic anastomosis has been performed. A robotic anastomosis is defined as having received at least 1 robotic suture as part of a study procedure. To assist in this determination, for the index procedure, for each anastomosis attempted, the number of robotic sutures will be classified as follows from CRF data:

0 (zero) robotic sutures

≥ 1 robotic sutures (minimum requirement for inclusion in the Safety Analysis Set (SAS) and the FAS)

If the number of robotic sutures is missing, then the anastomosis will be classified as robotic provided the following criteria are met:

The response to the question 'How did you intend to perform the anastomosis?' = 'Robotic **and**

The response to the question "Did you experience any system technical issues resulting in unplanned return to conventional suturing"? = "No".

If at least one anastomosis is classified as robotic (as defined above) the patient will be considered treated robotically and will be included in the FAS for assessment of effectiveness.

The FAS will form the basis of all summarization and analysis of effectiveness variables. However, for each effectiveness variable, the data summary and analysis will only include patients that have non-missing data for the effectiveness outcome being analyzed. The number of patients included in the analysis/summary will be clearly indicated in each tabular presentation.

2.2.2.2 Subpopulations of the FAS.

Two distinct sub-populations will be defined based on the FAS.

- The prospective patient sub-population

Sponsor: MMI Product: Symani system for microsurgical anastomosis Study: PRIMO	
Statistical Analysis Plan Final 22 November 2024	

- The retrospective patient sub-population.

All summaries and analyses will be presented using all data combined and by sub-population.

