2.4.4.3.1 Free-flap survival rate at 30 days

As per section 2.1.3.5.1 each flap for each patient in the FAS will be assigned to 'Yes' or 'No' for free flap survival at 30 days. This represents a binary outcome. The analysis of this variable is at the procedure (flap) level. Summary and analysis will be as described above for flap loss/failure (Model 4).

Sponsor: MMI Product: Symani system for microsurgical anastomosis Study: PRIMO	
Statistical Analysis Plan Final 22 November 2024	

In addition, the effectiveness of the Symani System will be evaluated for consistency with the free flap success rates reported in the UK National Flap Registry [1], where the overall free flap survival rate was 96.0% (95% confidence limits, 95.4%, 96.6%)."

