2.5.5 Windows for time points

All data are expected to be collected within a timeframe of 30 \pm 7 days from the initial study procedure (or 24 weeks \pm 2 weeks for lymphatic surgery). If a patient has a revision procedure where the revision is to a robotic anastomosis, then the timeframe for data collection will be 30-days from the date of the last revision procedure (revision to a robotic anastomosis), where the date of re-operation is prior to the date of discharge. However, for the retrospective data collection, available data will be used whenever possible. Data may not be available at 30 days post-operation.

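### The 30-day free flap viability rule never treats a recorded loss as final, so known early losses can drop out and the survival compared with the registry's 96.0% can be biased in either direction

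*SAP*

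**What the plan says.** SAP 2.1.3.5.1 sets out a hierarchy for each flap and applies the same one to replantations.

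1. A late form is defined first: "If there is a form where the visit is at least 23 days post index operation". Then: "If there is a 30-day follow-up form with a non-missing answer to the question, this response will be used".
2. If there is no such answer and the patient died, "the last recorded flap survival status will be used, regardless of when this was recorded".
3. If there is no such answer and the termination form shows exit for another reason, "the last recorded flap survival status will be used, provided the status was recorded ≥ 20 days since the index procedure".
4. "Otherwise, in all other circumstances the endpoint will be set to missing".

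Missing outcomes are not imputed. Under SAP 2.2.2.1, "the data summary and analysis will only include patients that have non-missing data for the effectiveness outcome being analyzed", and SAP 2.5.2 says the same in general terms.

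SAP 2.4.4.3.1 then sets the resulting survival rate against the UK National Flap Registry, "where the overall free flap survival rate was 96.0" per cent, with 95% limits of 95.4% and 96.6%. No test, margin or decision rule is attached. For retrospective patients, SAP 2.5.5 warns: "Data may not be available at 30 days post-operation".

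**The concern.** A lost flap stays lost. A loss on day 4 settles the day-30 answer, whereas a flap seen alive on day 4 does not. The hierarchy gives both records the same shelf life, so some observed failures are treated as unknown. It also lets a late 'No' to flap loss silently replace an earlier 'Yes'.

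The SAP is not consistent with itself here. A day-4 loss counts if the patient later dies but not if the patient withdraws alive. For re-admission and re-operation (2.1.5.1.3 and 2.1.5.1.4), a 'Yes' on any form makes the patient an event, and the earliest date is used. A flap with zero survival at discharge is a failure under 2.1.3.3.2, yet the same flap can be missing at 30 days, so reported 30-day survival could exceed survival at discharge.

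At stake is the only flap survival figure that the SAP compares with the registry. SAP 2.5.5 and 2.5.6 both expect gaps in the retrospective data, so the missing branch will probably be used.

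**Working it through.** **Which flaps are affected.** Take a flap recorded as lost on day 4 with no later status.

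| Situation | Result under 2.1.3.5.1 |
|---|---|
| Answered form at day 23 or later says lost | Failure, kept |
| Answered form at day 23 or later says not lost | Survival; earlier loss overridden |
| No such form, patient died | Failure, kept |
| No such form, exit for another reason | Missing |
| No such form, no early-exit record | Missing |

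A flap last seen surviving on day 4 is missing in the same last two rows. The day-20 fallback also needs a termination form showing non-completion; without one, even a status from days 20 to 22 is missing.

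**Registry figure.** The registry counts are not in the documents, so 96.0% cannot be reproduced. The limits are symmetric at ±0.6 points. Under a normal interval that corresponds to n ≈ 0.96 × 0.04 / (0.006/1.96)² ≈ 4,098. The half-width of 0.6 points serves below as a yardstick.

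**Effect of the rule.** Let S be true 30-day survival, ms the share of surviving flaps set to missing, and ml the share of lost flaps set to missing. The documents give none of these; all values are assumptions.

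Reported survival = S(1 − ms) / [S(1 − ms) + (1 − S)(1 − ml)]

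With S = 94%:

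| ms | ml | Calculation | Reported |
|---|---|---|---|
| 10% | 50% | 0.846 / (0.846 + 0.030) | 96.6% |
| 10% | 30% | 0.846 / (0.846 + 0.042) | 95.3% |
| 10% | 10% | 0.846 / (0.846 + 0.054) | 94.0% |
| 20% | 5% | 0.752 / (0.752 + 0.057) | 93.0% |
| 30% | 10% | 0.658 / (0.658 + 0.054) | 92.4% |

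Reported survival is too high if ml > ms, correct if they are equal, and too low if ml < ms. At ms = 10% and ml = 50%, S = 92% gives 95.4% and S = 96% gives 97.7%.

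**In counts (assumed).** Suppose 200 flaps, 12 lost by discharge, and 19 survivors without late follow-up. If 6 losses also lack it, reported survival is 169/175 = 96.6%, against 188/200 = 94.0% at discharge. With 3 such losses it is 169/178 = 94.9%; with 1 it is 169/180 = 93.9%. With no survivors missing, one dropped loss moves 188/200 = 94.0% to 188/199 = 94.5%, close to the registry half-width.

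**The obvious repair also fails.** Suppose every loss counts but survivors still need late follow-up. The proportion becomes S(1 − ms) / [S(1 − ms) + (1 − S)]. At S = 94% this is 0.846/0.906 = 93.4% for ms = 10% and 0.752/0.812 = 92.6% for ms = 20%. Both are too low.

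**The case against.** A reader might infer that reported survival is necessarily too high and flatters the device. The documents do not support that. The timing condition and the final catch-all do not distinguish lost from surviving flaps, and nothing states that patients who lose a flap leave earlier. SAP 2.5.5 even points partly the other way: after revision of a robotic anastomosis before discharge, collection runs 30 days from the last revision, so some troubled flaps may be followed longer. The retrospective gap affects survivors as well. This part of the objection stands in full.

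It can also be said that early losses remain visible elsewhere. The protocol-defined loss endpoint at discharge has no day-20 condition, complications are reported as adverse events, tables show the number missing (2.4.1), and results are split into prospective and retrospective patients. That is correct and lowers the weight of the point. But the missing count does not show how many of those flaps are known losses, and the discharge endpoint carries no registry comparison. Nor is there a sensitivity analysis here, although 2.1.5.1.1 plans a worst-case one for unclassified device-related serious events.

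The override is a contradictory record, and nothing suggests it would be common. When the earlier loss is true, however, it can only raise survival, and the SAP resolves the contradiction by default rather than by query.

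**Conclusion.** The rule discards observed failures, and that follows from the text without any assumption. The direction and size of the resulting bias are unknown. In the scenarios with assumed true survival of 94%, the reported figure runs from 92.4% to 96.6%, so the shift can exceed the registry's half-width of 0.6 points either way. These figures also treat every loss without late follow-up as one that was recorded and then dropped; a loss that nobody recorded would be unknown under any rule.

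The endpoint is additional to the protocol (SAP 1.5) and the comparison is descriptive, so the primary conclusion is untouched. The rule should still be corrected before 30-day flap survival is reported beside the registry figure.

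**What to change.** In SAP 2.1.3.5.1 and 2.4.4.3.1:

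- Count any recorded flap loss dated within the 30-day window as a failure, whatever follow-up comes later. Sources are the discharge question, any visit form, and the re-operation and adverse event forms.
- Resolve a later 'No' that contradicts an earlier 'Yes' by data query.
- Make the Kaplan-Meier estimate at day 30 the main figure for the registry comparison, with loss as the event and surviving flaps censored at their last recorded status. SAP 2.4.6.2.4 already uses this method for re-operation. It recovers true survival if censoring is unrelated to loss, which should be stated.
- As a check, give best- and worst-case bounds for flaps of unknown status. In the count example, with all 12 losses counted, these are 188/200 = 94.0% and 169/200 = 84.5%.
- Do not count all losses while still excluding early survivors from a simple proportion. Model 4 fitted to known statuses only would have the same weakness, so it should not carry the comparison.
- Apply the same rule to replantations.

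The cost is a few sentences and some reprogramming on data already collected. Reported survival may come out slightly lower.
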